The correlation between BCVA (letters) by ETDRS and Central Corneal ECD will be assessed by using Pearson's and Spearman's correlation coefficients. The correlation scatter plot will also be presented. The correlations and scatter plots will be based on data from all visits combined and analysed for all subjects overall as well as by each treatment arm. The correlations will be assessed separately using different data scenario:

- In the first correlation analysis, the data handling methods will be the same as primary analysis for [REDACTED] Central corneal ECD assessments, or the Central corneal ECD assessments that could not be performed due to oedema. Otherwise, the analysis will be [REDACTED]. Patients who receive a rescue keratoplasty will also be [REDACTED].
- The second correlation analysis will be the same as first except that the analysis visits where corneal oedema is observed or the Central corneal ECD assessments that could not be performed due to oedema will be [REDACTED].
- In the third analysis, the analysis visits where there are [REDACTED] Central corneal ECD assessments, or the Central corneal ECD assessments that could not be performed due to oedema will be [REDACTED]. Otherwise, the analysis will include the same data as the first correlation analysis.
- The fourth correlation analysis will be the same as third except that the analysis visits where corneal oedema is observed or the Central corneal ECD assessments that could not be performed due to oedema will be [REDACTED].

The BCVA (letters) by ETDRS will be summarized by the Central corneal ECD subgroups (defined below as sub-groupings (A) and (B)) at each visit and across all post-baseline visits by each treatment arm and all treatment arms combined. Box plots will also be presented for each at each visit and across all post-baseline visits by each treatment arm and all treatment arms combined for sub-grouping definition (A). Scatter plot and correlation coefficient (Spearman) will also be presented for each subgroup at each visit and across all post-baseline visits by each treatment arm and all treatment arms combined for sub-grouping definition (B). [REDACTED] Central corneal ECD include [REDACTED] Central corneal ECD assessments or the Central corneal ECD assessments that could not be performed due to oedema. Central corneal ECD assessments

that are [REDACTED] due to other reasons are [REDACTED]. Patients who receive a rescue keratoplasty will also be [REDACTED].

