**Table 14.2.1.49**  
Correlation between BCVA by ETDRS and Central Corneal ECD (Include [REDACTED]) (Pearson and Spearman)  
(Full Analysis Set)

|                        | K-321 QID
(N=XXX) | K-321 BID
(N=XXX) | Placebo
(N=XXX) | Total
(N=XXX) |
|------------------------|----------------------|----------------------|--------------------|------------------|
| Pearson's Correlation  | 0.XX                 | 0.XX                 | 0.XX               | 0.XX             |
| Spearman's Correlation | 0.XX                 | 0.XX                 | 0.XX               | 0.XX             |

Note: BCVA = Best Corrected Visual Acuity, ETDRS= Early Treatment Diabetic Retinopathy Study  
 ECD = Endothelial Cell Density  
 Central corneal ECD assessments that are unable to be performed due [REDACTED].  
 Ass [REDACTED] be a [REDACTED] ed an [REDACTED] s [REDACTED].  
 or [REDACTED] by [REDACTED] [REDACTED] [REDACTED].  
 Ass [REDACTED] are [REDACTED].

<DIRECTORY PATH>PROGRAM NAME Executed: DDMMYYYY hh:mm

Table 14.2.1.50

Correlation between BCVA by ETDRS and Central Corneal ECD (Include [REDACTED] Data) (No Corneal Oedema)  
(Pearson and Spearman)  
(Full Analysis Set)

Same format as Table 14.2.1.49

Note: BCVA = Best Corrected Visual Acuity, ETDRS= Early Treatment Diabetic Retinopathy Study  
ECD = Endothelial Cell Density

Assessments before and after rescue keratoplasty are [REDACTED] as [REDACTED]  
or [REDACTED] by [REDACTED] are [REDACTED].  
Only [REDACTED] a observation [REDACTED].  
Assessments after rescue keratoplasty are [REDACTED].

<DIRECTORY PATH>PROGRAM NAME Executed: DDMMYYYY hh:mm

Table 14.2.1.51

Correlation between BCVA by ETDRS and Central Corneal ECD (Exclude [REDACTED] Data) (Pearson and Spearman)  
(Full Analysis Set)

Same format as Table 14.2.1.49

Note: BCVA = Best Corrected Visual Acuity, ETDRS= Early Treatment Diabetic Retinopathy Study  
ECD = Endothelial Cell Density

Central corneal ECD assessments that are unable to [REDACTED] and a [REDACTED] s  
[REDACTED] be analysed and categorized as [REDACTED] or [REDACTED]  
[REDACTED] are not included.  
[REDACTED] rescue keratoplasty are [REDACTED].

<DIRECTORY PATH>PROGRAM NAME Executed: DDMMYYYY hh:mm

Table 14.2.1.52

Correlation between BCVA by ETDRS and Central Corneal ECD (Exclude [REDACTED] Data) (No Corneal Oedema)  
(Pearson and Spearman)  
(Full Analysis Set)

Same format as Table 14.2.1.49

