**Figure 14.2.1.48**  
BCVA by ETDRS by Central ECD Value by Visit (Scatter Plot)  
(Full Analysis Set)

Note: BCVA = Best Corrected Visual Acuity, ETDRS= Early Treatment Diabetic Retinopathy Study  
ECD = Endothelial Cell Density  
Baseline is defined as the last [redacted] measurement including unscheduled assessments prior to the administration of first dose of [redacted] ment.

[figure not shown]
Source Data: Table 14.2.1.48

DIRECTORY PATH>PROGRAM NAME Executed: DDMMYYYY hh:mm

Programming note: Please show x-axis according to the subgroups '1 < Central ECD Value <= Mean', 'Central ECD Value > Mean' 'and [REDACTED]'. Please display y-axis label as 'BCVA by ETDRS Letter Score'. Please display 'All Post-Baseline Visits' in the first page, then start the second page with 'Baseline', 'Week X'... Each visit should be on a separate page.

In each page please display all treatment groups: Total, K-321 QID, K-321 BID, Placebo  
In each page please include number of subjects under each treatment arm and subgroups under the plot.  
Please display the spearman correlation and p-value under the figure for each treatment group and total.

Figure 14.2.1.49  
Correlation between BCVA by ETDRS and Central Corneal ECD (Include [REDACTED] (Pearson and Spearman)  
(Full Analysis Set)

Note: BCVA = Best Corrected Visual Acuity, ETDRS= Early Treatment Diabetic Retinopathy Study  
ECD = Endothelial Cell Density  
Central corneal ECD assessments that are unable to be performed due [REDACTED].  
Ass [REDACTED] be a [REDACTED] ed an [REDACTED] s [REDACTED].  
or [REDACTED] by [REDACTED] [REDACTED] [REDACTED] [REDACTED].  
Ass [REDACTED] are [REDACTED] [REDACTED] [REDACTED].  
Source Data: Table 14.2.1.49

<DIRECTORY PATH>PROGRAM NAME Executed: DDMMYYYY hh:mm

Programming note: Please display x-axis label as 'Central Corneal ECD (cells/mm^2)'. Please display y-axis label as 'BCVA by ETDRS Letter Score'.  
Please display the scatter lot for total and each treatment group in separate pages.

Please include the spearman and perason correlation values and the corresponding p-values under the figure for each treatment group and total.

Figure 14.2.1.50

Correlation between BCVA by ETDRS and Central Corneal ECD (Include [REDACTED] Data) (No Corneal Oedema)  
(Pearson and Spearman)  
(Full Analysis Set)

Repeat Figure 14.2.1.49 but only include the visits where there is No Corneal Oedema.

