**Figure 14.2.1.51**  
Correlation between BCVA by ETDRS and Central Corneal ECD (Exclude [REDACTED] Data) (Pearson and Spearman)  
(Full Analysis Set)

Repeat Figure 14.2.1.49 but only include the visits where there is no imputed data.

Note: BCVA = Best Corrected Visual Acuity, ETDRS= Early Treatment Diabetic Retinopathy Study  
ECD = Endothelial Cell Density  
Central corneal ECD assessments that are unable to [REDACTED] and a [REDACTED] es  
[REDACTED] be analysed and categorized as [REDACTED] or [REDACTED]  
[REDACTED] are not included.  
[REDACTED] rescue keratoplasty are [REDACTED].  
Source Data: Table 14.2.1.51

<DIRECTORY PATH>PROGRAM NAME Executed: DDMMYYYY hh:mm

Programming note: Please display x-axis label as 'Central Corneal ECD (cells/mm^2)'. Please display y-axis label as 'BCVA by ETDRS Letter Score'.  
Please display the scatter lot for total and each treatment group in separate pages.  
Please include the spearman and perason correlation values and the corresponding p-values under the figure for each treatment group and total.

Figure 14.2.1.52

Correlation between BCVA by ETDRS and Central Corneal ECD (Exclude [REDACTED] Data) (No Corneal Oedema)  
(Pearson and Spearman)  
(Full Analysis Set)

Repeat Figure 14.2.1.49 but only include the visits where there is no imputed data and the visits where there is No Corneal Oedema.

Note: BCVA = Best Corrected Visual Acuity, ETDRS= Early Treatment Diabetic Retinopathy Study

ECD = Endothelial Cell Density

Ass [REDACTED] be analysed and categorized as [REDACTED]

or [REDACTED] are not included.

Only [REDACTED] a obs

Assessments after rescue keratoplasty are [REDACTED]

Source Data: Table 14.2.1.52

<DIRECTORY PATH>PROGRAM NAME Executed: DDMMYYYY hh:mm

Programming note: Please display x-axis label as 'Central Corneal ECD (cells/mm^2)'. Please display y-axis label as 'BCVA by ETDRS Letter Score'.

Please display the scatter lot for total and each treatment group in separate pages.

Please include the spearman and perason correlation values and the corresponding p-values under the figure for each treatment group and total.

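### The addendum's pooled BCVA–ECD p-values make no readable allowance for up to 12 scheduled visits per eye, so they are too small if both measures are positively correlated within a patient

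*SAP*

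**What the plan says.** Section 1 of the SAP addendum says that it describes analyses defined after the Week 12 unmasking, in support of the final study report. For BCVA letters against central ECD, Section 2 names Pearson's and Spearman's coefficients and adds: "The correlations and scatter plots will be based on data from all visits combined". This is done overall and by arm, in four data scenarios.

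The programming note to Figure 14.2.1.49, repeated for Figures 14.2.1.50 to 14.2.1.52, reads: "Please include the spearman and perason correlation values and the corresponding p-values under the figure for each treatment group and total". The shell of Table 14.2.1.49, which Tables 14.2.1.50 to 14.2.1.52 reuse, has one row for Pearson and one for "Spearman's Correlation", and no p-value row.

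Figure 14.2.1.48 also pools visits on one page: "Please display 'All Post-Baseline Visits' in the first page". For the remaining pages, "Each visit should be on a separate page". Its note continues: "Please display the spearman correlation and p-value under the figure for each treatment group and total". For the same output, Section 2 asks for the Spearman coefficient to be "presented for each subgroup at each visit and across all post-baseline visits".

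No readable text names a mixed model, a patient-level bootstrap or any other method for repeated visits. The sentences that name the coefficients and pool the visits are not redacted. The blacked-out text around them concerns which assessments are kept and how they are handled. Primary SAP v2.0 is not among the documents.

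**The concern.** The usual p-value for a Pearson or Spearman coefficient assumes independent rows. Here the rows are repeated measurements of one eye per patient, up to 12 of them. If patients with a high ECD at one visit tend to have a high ECD at others, and BCVA behaves likewise, the pooled rows carry less information than their number suggests.

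A reader of the study report could then take a small p-value as strong evidence that ECD, the primary endpoint measure, goes with vision, when it partly reflects measuring the same eyes many times. Clustering in itself does not bias the coefficients; the p-values are what go wrong.

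**Working it through.** The plan states no sample size, power or error rate for these correlations, so there is no figure of its own to reproduce.

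**Inputs from the documents**
- Protocol Table 6-1: BCVA and specular-microscopy ECD are both marked at Visit 1 and Visits 4 to 14, so m = 1 + 11 = 12 pairs per study eye. The optional Week 2 visit makes 13. The post-baseline page of Figure 14.2.1.48 has 11 scheduled pairs.
- Protocol Sections 4.1 and 7.4: about 60 patients, 20 per group. The maximum is 60 × 12 = 720 rows in total and 20 × 12 = 240 per arm.
- Protocol Section 7.7: two-sided tests at 0.05.

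**Assumed inputs.** The within-patient correlations ρx (ECD) and ρy (BCVA) are not given. The range 0 to 0.7 is used, equal between any two visits, with no true association.

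**Formulas**
- Variance factor of the pooled coefficient: D = 1 + (m − 1)·ρx·ρy
- Effective rows: N·m / D
- Actual size of the nominal 5% test: 2·[1 − Φ(1.96/√D)]

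For m = 12 and both correlations 0.5: D = 1 + 11 × 0.25 = 3.75; effective rows = 720/3.75 = 192; size = 2·[1 − Φ(1.01)] = 31.1%.

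| ρx = ρy | D | Effective rows (of 720) | Size, formula | Simulated, 60 patients: Pearson / Spearman | Simulated, 20 patients: Pearson / Spearman |
|---|---|---|---|---|---|
| 0 | 1.00 | 720 | 5.0% | 4.5% / 5.5% | 5.3% / 5.3% |
| 0.3 | 1.99 | 362 | 16.5% | 15.9% / 15.9% | 16.4% / 14.1% |
| 0.5 | 3.75 | 192 | 31.1% | 31.5% / 31.6% | 31.4% / 28.9% |
| 0.7 | 6.39 | 113 | 43.8% | 44.4% / 42.5% | 44.8% / 43.7% |

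The simulations used 4,000 null trials for Pearson and 1,500 for Spearman.

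**Other settings** (three values are for ρ = 0.3 / 0.5 / 0.7)
- 13 pairs: D = 2.08 / 4.00 / 6.88; size 17% / 33% / 46%.
- 11 pairs: D = 1.90 / 3.50 / 5.90; size 15.5% / 29.5% / 42.0%; simulated Spearman 15.7% / 28.5% / 41.3%.
- 6 pairs, for illustration: D = 1.45 / 2.25 / 3.45; size 10% / 19% / 29%.
- Unequal correlations 0.3 and 0.7, 12 pairs: D = 1 + 11 × 0.21 = 3.31; size 28%.
- Correlations 0.7 and 0: D = 1; size 5% (simulated Pearson 4.6%).
- Serial correlation, 0.8 between adjacent visits, 12 pairs, 60 patients: simulated 29.6%.

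**What a printed p-value would mean.** With 720 rows, r = 0.073 prints p = 0.05. On 362 / 192 / 113 effective rows, the same r has p of about 0.17 / 0.31 / 0.44.

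**Does patient-level inference repair it?** With 12 visits and no association, a percentile bootstrap that resamples patients wrongly excluded zero for the pooled Pearson r in 6.8% / 6.0% / 5.2% of trials with 60 patients and 7.2% / 8.5% / 8.0% with 20 (2,000 trials, 1,000 resamples each). Its half-widths were 0.10 / 0.13 / 0.18 against a naive 0.07, and 0.16 / 0.21 / 0.28 against 0.13. Permuting whole patients gave 4.8% to 5.3%, and one visit per patient 4.4% to 5.1%, over correlations of 0.3 to 0.8.

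**The case against.** Four points can be made on the other side.

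- **Twelve pairs is a ceiling.** Figures 14.2.1.50 to 14.2.1.52 restrict the visits; for Figure 14.2.1.52 the instruction is "Repeat Figure 14.2.1.49 but only include the visits where there is no imputed data and the visits where there is No Corneal Oedema". This stands. The documents do not show how many visits remain, and the inflation shrinks with fewer, as the six-pair case shows.
- **Clustering is not the only problem.** All eyes are followed from before surgery through healing, so ECD and BCVA may share a visit trend. In a simulation of 400 trials with no association between patients or within a visit, a shared linear trend carried 10% of each measure's variance. The patient bootstrap interval then excluded zero in 60% / 40% / 27% of trials at correlations of 0.3 / 0.5 / 0.7. This stands as a limit on interpretation: the pooled coefficient really is non-zero in that setting, so the interval is not in error, but the coefficient mixes time with association between patients. It does not rescue the naive p-value.
- **The figures for the pooled page of Figure 14.2.1.48 are less secure.** They assume one coefficient over all post-baseline rows. If the coefficient is computed within ECD subgroups, fewer rows per patient enter. This stands too, and arises from the mismatch between Section 2 and the figure note.
- **The outputs are openly post hoc.** They compare no treatments, and Protocol Section 7.7 disclaims error control for multiple secondary and exploratory endpoints. That lowers the stakes. But lack of multiplicity control is a different matter from a p-value computed on the wrong unit.

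**Conclusion.** The concern holds. Following the shells as written, with ordinary p-values, gives p-values that are too small in Figures 14.2.1.49 to 14.2.1.52 and on the pooled page of Figure 14.2.1.48 whenever both measures are positively correlated within a patient. That condition is plausible for repeated measurements of one eye.

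The direction is established under that condition; the size is not. The rejection rates of about 16% to 44% rest on assumed correlations of 0.3 to 0.7 and all 12 scheduled visits being present. The single-visit pages of Figure 14.2.1.48 hold at most one pair per patient and are unaffected. Primary SAP v2.0 could contain a general rule on repeated measures, so the finding is that no allowance is readable. The correction is worth making but concerns supportive outputs only.

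**What to change.** 1. Remove the pooled p-values from Figures 14.2.1.49 to 14.2.1.52 and from the all-post-baseline page of Figure 14.2.1.48. For the former this also brings the figures into line with their tables.
2. If inference is wanted, make the patient the unit. A bootstrap that resamples patients keeps the planned coefficient; label the per-arm intervals approximate, since they rest on 20 patients. A mixed model of BCVA on ECD with patient and visit effects is an alternative, but it estimates a visit-adjusted slope instead.
3. Label every pooled coefficient descriptive, and say that it combines changes over time with differences between patients.
4. Reconcile Section 2, which asks for the Spearman coefficient by ECD subgroup, with the Figure 14.2.1.48 note, which asks for it by treatment group and total. The result should include an overall by-visit coefficient with one point per patient.

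The cost is addendum wording and a little programming, with no new data. Overall intervals become about 1.4 to 2.4 times as wide as the naive ones under the assumed correlations (ratios taken before rounding). By-visit coefficients rest on at most about 60 points, or about 20 per arm.

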4.1 Selection of Study Population

Approximately 60 patients will be enrolled at approximately 30 sites in the United States, Europe, and Australia. Patients will be assigned to study treatment only if they meet all of the inclusion criteria and none of the exclusion criteria.

Deviations from the inclusion and exclusion criteria are not allowed because they can potentially jeopardise the scientific integrity of the study, regulatory acceptability, or patient safety. Therefore, adherence to the criteria as specified in the protocol is essential. Rescreening of patients that failed the initial screening may be done if the patient fulfils selection criteria upon a subsequent visit. However, this may only be done for some of the criteria, as specified below.

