4.1.1 Inclusion Criteria

Each patient must meet all of the following criteria to be enrolled in this study:

1. Is at least 18 years old at the screening visit (Visit 1). – Re-screening possible if initial screening was soon before 18th birthday.
2. Has a diagnosis of FECD at Visit 1. – Rescreening is not possible.
3. Has confluent central guttae in the study eye that can be removed by descemetorhexis of a circular area of [REDACTED] diameter or less (at Visit 1). – Rescreening is not possible.
4. Has a study eye with best corrected visual acuity (BCVA) of 75 letters or fewer by Early Treatment Diabetic Retinopathy Study (ETDRS) testing (Snellen equivalent of 20/32 or worse) at Visit 1. – Rescreening is not possible.
5. The study eye descemetorhexis at Visit 2 is confirmed to have excised a central area with confluent guttae and a diameter of [REDACTED]. Guidance for performing the study eye descemetorhexis and measurement of the excised area will be provided in the study manual. – Rescreening is not possible in that eye but the non-study eye can be used.

6. Can understand the written informed consent, provides signed and witnessed written informed consent, and agrees to comply with protocol requirements before any study-specific assessment is performed. – Rescreening is not possible.

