7.4 Sample Size Calculations

A sample size of 20 patients in each group will be needed to detect a difference of [REDACTED] in the measurement in the corneal ECD at Week 12 between K-321 0.4% QID/BID and placebo groups with a power of [REDACTED] for Step 1 and a power of [REDACTED] for Step 2 using a Wilcoxon rank sum test with a 0.050 two-sided significance level with closed testing procedures. Sample size was calculated by simulation. For the simulation, based on the existing literature ([Borkar DS, et al. 2016](#), [Moloney G, et al. 2017](#), [Iovieno A, et al. 2017](#)), placebo was assumed to be distributed normally with [REDACTED]

and K-321 was assumed to be distributed normally with [REDACTED]. Proportion of unmeasurable value of Week 12 due to corneal oedema and proportion of [REDACTED] value of Week 12 due to the withdrawal were assumed to be about 10% and about 5%, respectively. Here, unmeasurable value of Week 12 due to corneal oedema were imputed as zero, and [REDACTED] value of Week 12 due to the withdrawal were imputed by the last-observation-carried-forward (LOCF) method.

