7.7 Statistical Analysis Methodology

Statistical analysis will be performed using SAS software Version 9.4 or later. Continuous variables will be summarised using the mean, the SD, median, minimum value, and maximum value. Categorical variables will be summarised using frequency counts and percentages. Unless otherwise noted, the denominator to determine the percentage of participants in each category will be based on the number of participants with available data. Selected ordinal data may be summarised using both descriptive statistics and counts and percentages of participants in each category, as appropriate. Data will be listed in data listings.

Details of the statistical analyses, methods, and data conventions are described in the statistical analysis plan (SAP).

All statistical tests will be 2-sided and performed using a 0.05 significance level, leading to 95% (2-sided) CIs.

A closed 2-step ordered testing procedure will be used to control overall type I error for the primary efficacy endpoint, central corneal ECD at Week 12. In step 1, the K-321 0.4% QID group will be statistically compared with the placebo group. If the step 1 comparison is significant, step 2 will be performed to statistically compare K-321 0.4% BID group with the placebo group. If the statistical comparison made during step 1 is not significant, testing will still be performed to compare the BID group to placebo; however, all p values will be considered nominal/descriptive only.

No other measures will be taken to control error for the multiple secondary and exploratory endpoints or multiple treatment comparisons.

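### The BCVA-ECD correlations pool all visits with no adjustment for visit or patient, so they mix recovery over time with the ECD-vision relation and their p-values are not valid

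*SAP*

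**What the plan says.** Section 2 of the SAP addendum has the relation between BCVA and central ECD "assessed by using Pearson's and Spearman's correlation coefficients". On which data enter, it says: "The correlations and scatter plots will be based on data from all visits combined and analysed for all subjects overall", with the same analysis repeated in each arm. The four analyses differ in how they treat imputed ECD values and visits with oedema, and all four pool over visits.

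The shell for Table 14.2.1.49 has one Pearson and one Spearman value per column, with no row or term for visit. Tables 14.2.1.50 to 14.2.1.52 use the same format. The programming note under Figure 14.2.1.49, repeated under the next three figures, reads: "Please include the spearman and perason correlation values and the corresponding p-values under the figure for each treatment group and total". No method for repeated measurements on the same patient is visible.

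The next paragraph of Section 2 plans BCVA summaries by ECD subgroup "at each visit and across all post-baseline visits by each treatment arm and all treatment arms combined". For sub-grouping (B) it also plans scatter plots and Spearman coefficients within each subgroup (Table and Figure 14.2.1.48).

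**The concern.** Descemetorhexis removes the central endothelium. The protocol then follows its return, with time to an ECD of 700 cells/mm² among the secondary endpoints (Section 7.2) and time to a BCVA letter score among the exploratory ones (Section 7.3). If both measures rise over the year, early visits tend to be low on both and late visits high on both. One coefficient over all visits then adds this shared time course to whatever association exists between eyes at the same visit.

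There are two consequences. The coefficient itself can be distorted, so it cannot show on its own whether eyes with more cells see better. The p-values treat up to 12 pairs from one patient as 12 independent pairs, which is wrong even without a time trend. At stake is how the final study report describes ECD as a marker of vision.

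**Working it through.** The documents state no correlation figure, so there is none to reproduce.

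**Inputs from the documents**
- Patients: "Approximately 60 patients will be enrolled" (Protocol 4.1). Per arm: "A sample size of 20 patients in each group will be needed" (Protocol 7.4). 3 × 20 = 60.
- Visits with both ECD and BCVA (Table 6-1): Visit 1 and Visits 4 to 14, so 1 + 11 = 12 scheduled visits, or 13 with the optional Week 2 visit.
- Pairs: 60 × 12 = 720 in total (60 × 13 = 780 at most) and 20 × 12 = 240 per arm.
- Level: "All statistical tests will be 2-sided and performed using a 0.05 significance level" (Protocol 7.7).
- Pre-operative vision: "best corrected visual acuity (BCVA) of 75 letters or fewer" (Protocol 4.1.1, criterion 4).

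**Mechanism.** With equal numbers at each visit, within-visit SDs σx and σy, within-visit correlation ρ, and visit means mx and my:

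r(pooled) = [ρσxσy + Cov(mx, my)] / √{[σx² + Var(mx)] × [σy² + Var(my)]}

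Illustration with assumed values: half the pairs at mean ECD 200 and BCVA 60, half at 600 and 70, with SDs of 250 cells/mm² and 12 letters. The visit means then have SDs of 200 and 5, and covariance 200 × 5 = 1,000. The denominator is √[(62,500 + 40,000) × (144 + 25)] = 4,162.
- ρ = 0: r = 1,000 / 4,162 = 0.24.
- ρ = 0.30: r = (0.30 × 250 × 12 + 1,000) / 4,162 = 1,900 / 4,162 = 0.46.

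Centring within visit sets both between-visit terms to zero and returns ρ.

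**Simulation.** 60 patients, 12 visits, 400 runs per setting, with ECD and BCVA independent at every visit. All curves and SDs are assumptions: ECD plateau 700 to 800 cells/mm², SD 250 to 300; BCVA dip of 0 to 20 letters and then recovery, SD 10 to 14; within-patient correlation 0.6; unmeasurable ECD falling from 90% at Week 1 to 10%, and either set to 0 or excluded. Mean pooled Pearson r:

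| BCVA dip, baseline ECD | All visits, set to 0 | All visits, excluded | Post-operative, set to 0 | Post-operative, excluded |
|---|---|---|---|---|
| 20 letters, 700 | 0.40 | 0.24 | 0.44 | 0.28 |
| 20 letters, unmeasurable | 0.44 | 0.28 | 0.44 | 0.27 |
| 20 letters, 1500 | 0.28 | 0.04 | 0.44 | 0.27 |
| 10 letters, 700 | 0.24 | 0.12 | 0.27 | 0.14 |
| 10 letters, unmeasurable | 0.29 | 0.14 | 0.27 | 0.13 |
| 10 letters, 1500 | 0.14 | -0.03 | 0.27 | 0.14 |
| 10 letters, 2000 | 0.09 | -0.09 | 0.27 | 0.13 |
| 5 letters, 700 | 0.08 | 0.03 | 0.10 | 0.02 |
| 5 letters, 1500 | 0.02 | -0.09 | 0.11 | 0.04 |
| none, 700 | -0.01 | 0.00 | 0.00 | 0.00 |

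Spearman was mostly similar; the largest gap was for a 10-letter dip with baseline 2000 (0.17 against 0.09, all visits, set to 0). After centring or ranking within visit, the mean coefficient lay between -0.01 and 0.01 in every setting.

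**Pre-operative visit.** It pairs an intact centre with vision of 75 letters or fewer. Where its ECD is high and its BCVA below the later average, it adds a negative term to Cov(mx, my). In the table it lowers r in nearly every row with a measurable baseline and barely changes it where baseline is unmeasurable.

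**P-values.** With flat BCVA, so no time trend in vision, unadjusted tests at 0.05 rejected in 14% to 27% of runs. On visit-adjusted pairs they still rejected in 18% to 37%. Visit adjustment and patient-level clustering are both needed.

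**The case against.** - **Per-visit output is already planned.** This is true in part. Figure 14.2.1.48 has one page per visit with a Spearman coefficient, and the tables by visit show both time courses. But Section 2 specifies those coefficients within ECD subgroups split at the mean, which restricts the range of ECD. The programming note mentions only treatment group and total, so the scope is also unclear. No visible output gives a visit-adjusted coefficient over the whole ECD range.
- **Recovery may be part of the relation.** The protocol introduction links low ECD to oedema and haze, so change over time is not purely a confounder. This stands as a reason to keep a pooled coefficient if it is labelled as including change over time. It is no reason to report it alone.
- **The simulated sizes rest on assumed curves.** This stands, and it is why a range is given.
- **Stronger readings.** A reader might infer that a positive correlation is bound to appear. Without trajectories in the documents that does not follow: some settings gave values near zero or negative. A reader might also blame the pre-operative visit for a positive artefact, but it mostly works the other way, and its inclusion is inferred from the contrast between all visits and post-baseline visits. Nor does the distortion survive every repeated-measures analysis: a model with visit as a fixed effect removes it.

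**Conclusion.** The point holds in a limited form. The pooled coefficients combine a between-visit time course with the within-visit association, and nothing in the visible plan separates them. With no association at any visit, pooled Pearson r ran from about -0.09 to 0.44, depending on assumed recovery curves, SDs, baseline ECD and handling of unmeasurable values. The p-values on about 720 pairs are invalid with or without a time trend, because the pairs are clustered within about 60 patients.

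The reach is modest. Section 1 of the addendum says these analyses were defined after the Week 12 unmasking to support the final study report. They do not touch the primary test or any treatment comparison, and the documents do not say that they are meant to validate ECD as an endpoint.

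**What to change.** In Section 2 and the shells for Tables and Figures 14.2.1.49 to 14.2.1.52:
- State that the pooled correlations use post-baseline visits only. This step alone would tend to raise a positive artefact, so it must go together with the visit adjustment.
- Report coefficients over the full ECD range at Week 12 and at Week 52.
- Add one visit-adjusted coefficient, with both variables or their ranks centred within visit, or from a model with visit as a fixed effect.
- Take p-values or confidence intervals from a method that clusters by patient, for example a bootstrap that resamples patients.
- Colour the scatter plots by visit.
- If the pooled coefficient is kept, label it as including change over time.

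The cost is addendum wording and a few lines of programming. The reported correlations will probably be smaller and the p-values less extreme.
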